1 INTRODUCTION

1.1 Background

The COVID-19 Pandemic has led to over 100 million cases worldwide. In the UK alone, there have been over 4 million cases, over 400 thousand hospital admissions and over 100 thousand deaths. A large number of people diagnosed with COVID-19 suffer from long-term symptoms, predominantly breathlessness and fatigue whether or not they were admitted to hospital. However, long-term symptoms following COVID-19 are more common in people who suffered more severe acute disease [1-4]. There are a number of potential causes of long-term breathlessness following COVID-19 including thromboembolic disease, myo- or pericarditis, and physical deconditioning. However, based on early data from the COVID-19 pandemic, and from other viral infections, a common and potentially severe long-term consequence of COVID-19 is the development of Post COVID related Interstitial Lung Disease (PC-ILD) [5-7].

SARS-CoV-2 leads to pronounced inflammation within the lung and leads to the development of Acute Respiratory Distress Syndrome (ARDS) in a substantial proportion of those infected. Whilst data demonstrate that a short course of corticosteroids can improve survival in patients with hypoxia there is considerable evidence of longer-term inflammation even following short-term corticosteroid therapy [8]. Whilst the inflammatory potential of SARS-CoV-2 is well described, the fibrogenic potential of SARS-CoV-2 is currently unknown but is predicted to be substantial based on the experience of previous coronavirus outbreaks and emerging data from this pandemic [3, 7, 9]. Initial observations have identified substantial levels of post-COVID related ILD (PC-ILD) with up to 24% patients having fibrotic changes, on their initial CT scan, which do not appear to regress at longer time points. Similarly, between 18 - 34% of patients had lung function impairment following COVID-19, consistent with restrictive disease [7]. Risk factors for severe COVID-19 include increasing age, male sex and comorbidities including hypertension and type 2 diabetes mellitus [10, 11], which are also associated with progressive lung fibrosis [10-12].

Pilot data from our consortium indicate that novel functional imaging methods utilising 129Xe and 1H MRI are sensitive to gas transfer limitation, microstructural airway changes and alveolar perfusion deficit in both acute and long COVID patients. These methods also have some ability to dissect both inflammatory and fibrotic pathophysiology and are highly sensitive to disease progression in established ILDs [13-17].

1.2 Study Rationale

Given the large number of patients infected with SARS-CoV-2, it is vital that the extent of PC-ILD is determined; its natural history defined particularly whether it is time-limited inflammation and reversible, or develops into persistent, or even progressive, fibrosis. Determining the natural history of PC-ILD, and risk factors as well as biomarkers related to outcome such as disease progression, will enable a precise approach to treatments such as immunomodulation or antifibrotic therapy [6], stratification into clinical trials, prognostication and appropriate service provision. This will facilitate assessment and prioritisation of both conventional and novel therapies used in the treatment of COVID-19 during the acute phase to mitigate the subsequent development of PC-ILD. By exploring the long-term implications of SARS-CoV-2 infection across the full spectrum of COVID-19 disease ranging from non-hospitalised patients managed in the community with mild symptoms to those requiring mechanical ventilation, we will define the risk factors for PC-ILD including disease severity, host genetic factors and the effects of antiviral and immunomodulatory treatment administered during the acute phase of the illness. The UKILD Post COVID study is a prospective multicentre observational cohort study that will be managed through the Imperial College National Heart and Lung Institute and funded by the UKRI Medical Research Council and an NIHR professorship ([name]).

The PHOSP COVID study (ISRCTN10980107) is a national consortium that provides a platform to study the long-term consequences of COVID-19 hospitalisations [18]. An expected 10,000 individuals hospitalised by COVID-19 are to be included in baseline assessments after testing positive on PCR for SARS-CoV-2 and will be recruited through the PHOSP platform. The study described here will aim to recruit a further 2000 individuals, with proven COVID-19, who were not hospitalised but presented to Long-COVID clinics with persistent respiratory symptoms such as breathlessness or cough and are referred for cross-sectional imaging (computer tomography, CT) at baseline (3 months weeks after their first COVID-19 symptoms) [19]. A total of up to 12,000 people will be assessed for longitudinal follow up into the UKILD-Post COVID study. Following assessment of Post COVID patients at baseline (~3-6 months post infection as defined above), those with clinical and radiological features suggestive of ILD will be included into the UKILD-Post COVID study population. Where there are contraindications for CT and if clinically indicated, participants will be eligible for a research-guided 3D ultrashort echo time (UTE) proton MRI as a surrogate for CT. Where individuals meet criteria for initial study inclusion (COVID-19 and clinical indication for CT scanning) but have no clinical, radiological or physiological features of ILD they will be invited to enroll as part of the control cohort for follow up.

This protocol details the research partnership between Imperial (BREATHE Respiratory hub partner), and partner organizations.

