2.4 The secondary endpoints

- 1) progressive lung function impairment between 3 and 12 months, defined as $\geq 10\%$ relative decline in FVC, or $\geq 10\%$ relative decline in DLco, or increasing radiological extent of PC-ILD using image analysis [20].
- 2) Resolution of ILD, as defined by $\geq 10\%$ relative improvement in FVC, DLco, or reduction of radiological extent.

- 3) Persistence of ILD in those not meeting definition of progression or resolution
- 4) Presence of interstitial lung abnormalities (ILA) on radiological images that do not meet definition of ILD.
- 5) A comprehensive series of clinical, molecular, MRI and biochemical parameters will be assessed as biomarkers.

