3 STUDY DESIGN

Prospective observational study of hospitalised and non-hospitalised patients post- infection with SARS-CoV-2. The study aims to recruit 2000 individuals, with proven COVID-19, who were not hospitalised but presented to Long-COVID clinics with persistent respiratory symptoms such as breathlessness or cough and are referred for cross-sectional imaging (computer tomography, CT) at baseline (3 months weeks after their first COVID-19 symptoms). The study will run for 18 months.

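### Section 1.2 defines the ILD population and the control cohort so that people with only some features of ILD belong to neither, in conflict with sections 4.2 and 7

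*Combined protocol and SAP*

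**What the plan says.** Section 1.2 (Study Rationale) sets two rules at baseline.

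- ILD group: "those with clinical and radiological features suggestive of ILD will be included into the UKILD-Post COVID study population".
- Controls, among people with COVID-19 and a clinical indication for CT: those who "have no clinical, radiological or physiological features of ILD they will be invited to enroll as part of the control cohort for follow up".

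The same section describes the non-hospitalised recruits as people "who were not hospitalised but presented to Long-COVID clinics with persistent respiratory symptoms such as breathlessness or cough". Section 3 repeats this. What counts as a clinical feature of ILD is not defined anywhere.

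Other sections bear on who is followed and compared:

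- Section 2.4 lists as a secondary endpoint "Presence of interstitial lung abnormalities (ILA) on radiological images that do not meet definition of ILD".
- Section 3.1 makes the comparison of ILD prevalence between non-hospitalised and hospitalised patients primary, and asks for two time points six months apart.
- Section 4.2 admits people to Tier 2 on proven infection and a clinical indication for chest CT, and to Tier 1 on proven infection with breathlessness, a CT indication, or both. Neither tier requires a feature of ILD, and neither assigns anyone to an ILD or control cohort.
- Sections 3.2.1 and 5.1 mention matched controls at the optional Visit 2 without defining them.
- Section 7 assesses prevalence in the total study population and groups biomarker analyses by presence or absence of PC-ILD at 10-15 months. It takes internal risk-factor controls from participants who do not have the sequela under study, adds external controls, and leaves the choice of controls to each research question.

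**The concern.** The ILD rule needs two kinds of feature together, while the control rule needs all three kinds to be absent. Anyone in between has no group under section 1.2. That middle is not a technicality: it holds people with restrictive lung function and a clear CT, people with CT abnormality but no clinical features (including some ILA, which the study means to count), and people with clinical features and a clear CT.

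Two results are at stake. The first is the primary prevalence. Section 1.2 uses the term study population for people selected because they look as if they have ILD, and section 7 uses a similar term for the denominator. If the two mean the same, the denominator is chosen on features of the outcome. The second is the baseline contrast of biomarkers and risk factors. Comparing people who have clinical and radiological features with people who have none leaves out the range in which a biomarker has to discriminate in practice.

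The non-hospitalised stream adds a further doubt. Its members are described as symptomatic, so whether they can be controls turns on an undefined term.

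**Working it through.** **The plan's own total.** Section 1.2 gives an expected 10,000 hospitalised people through PHOSP and a further 2,000 non-hospitalised. 10,000 + 2,000 = 12,000, which matches the stated total of up to 12,000 to be assessed. That figure is not in dispute. No power or sample-size calculation bears on this point.

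**Enumerating the rules.** Let C, R and P stand for clinical, radiological and physiological features of ILD (1 = present). Section 1.2 then reads: ILD group if C = 1 and R = 1; control if C = R = P = 0.

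| C | R | P | Group under section 1.2 |
|---|---|---|---|
| 1 | 1 | 0 | ILD |
| 1 | 1 | 1 | ILD |
| 0 | 0 | 0 | Control |
| 0 | 0 | 1 | None |
| 0 | 1 | 0 | None |
| 0 | 1 | 1 | None |
| 1 | 0 | 0 | None |
| 1 | 0 | 1 | None |

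The count is 2 + 1 + 5 = 8. No other section assigns the five.

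**Non-hospitalised recruits.** If breathlessness or cough counts as a clinical feature of ILD, all of them have C = 1. The four remaining rows give ILD when R = 1 and no group when R = 0; none is a control. If such symptoms alone do not count, C can be 0 and the stream can supply controls. The text does not settle which reading applies.

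**Side by side.**

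- *Section 1.2 against 4.2:* a breathless person with low FVC and a clear CT can enrol under 4.2 but has no place in follow-up under 1.2.
- *Section 1.2 against 7:* the same person, if free of ILD, is an acceptable internal control under 7 but not under 1.2.
- *Section 1.2 against 2.4:* ILA without clinical features is to be counted under 2.4 but has no group under 1.2.

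**Effect on prevalence.** Suppose N people are eligible and D have ILD at 12 months. If m people in the middle are left out, d of whom have ILD, the estimate becomes (D - d)/(N - m) instead of D/N. It rises when d/m is below D/N and falls when d/m is above it. The documents give neither m nor d, so neither the size nor the sign of the shift follows from them.

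**Whether the Background figures can supply m.** Section 1.1 gives fibrotic CT change in up to 24%, and says that "between 18 - 34% of patients had lung function impairment following COVID-19, consistent with restrictive disease". The share with impaired function but no fibrotic change lies between max(0, p - r) and min(p, 1 - r). With r = 0.24:

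- p = 0.18: from 0 to 0.18.
- p = 0.34: from 0.34 - 0.24 = 0.10 to 0.34.

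The range is 0% to 34%, and it covers only one of the intermediate patterns. It is too wide to size anything.

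**The case against.** The strongest reply is that section 1.2 is rationale and the operative text lies elsewhere. Section 4.1 requires participants to satisfy the approved inclusion and exclusion criteria, and those criteria ask for no ILD feature. Section 3.2.1 schedules Visits 1 and 3 for post-COVID patients generally, and section 3.3 collects clinical images for all COVID-19 patients through follow-up. Section 7 analyses by presence or absence of PC-ILD at the late time point, which is close to an exhaustive split, and its internal controls need only lack the sequela. Strict, feature-free controls can also be a legitimate choice for a biomarker contrast.

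Most of this stands. A reader might infer from section 1.2 that people with partial features are dropped and that early or late-emerging ILD among them is missed. The documents do not support that as a fact; it follows only if 1.2 overrides 4.2.

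A reader might also infer that the non-hospitalised stream can yield no controls, so that only people with ILD remain in it. That depends on treating breathlessness or cough as a feature of ILD, which is the less natural reading: section 1.1 also attributes breathlessness to thromboembolic disease, myo- or pericarditis and deconditioning. Moreover, the Tier 2 criteria do not themselves require symptoms.

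The reply does not remove the conflict. Section 1.2 is the only place that says who enters the study population and who is invited as a control for follow-up. Nothing states that 4.2 takes precedence, and section 7 does not say which population its denominator means.

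**Conclusion.** The point holds as an unreconciled conflict between sections 1.2, 4.2 and 7. The gap in 1.2 is a matter of logic: five of eight feature combinations have no group, whatever their frequency.

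The consequences are conditional. They arise if sites or analysts apply 1.2 literally and if the section 7 denominator means the population described there, with or without its control cohort. The 12-month prevalence is then selected on features of the outcome, and the baseline case-control contrast compares extremes. That contrast would be exaggerated on the assumption that people with partial features have intermediate values. If 4.2 governs, the exclusion does not occur.

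No size can be attached. It is tempting to build one from the Background percentages, but the 24% is an upper figure for fibrotic change only, whereas the primary endpoint in section 2.3 includes non-fibrotic ILD. The overlap between CT change and impaired function is not given, independence between them is implausible, and the lower bound on the affected share is 0%.

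The point is still worth acting on during recruitment, because people never followed cannot later supply the two time points that section 3.1 requires.

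**What to change.** Reword section 1.2 and align section 7 with it:

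1. State that everyone who meets the section 4.2 criteria is in the study population, and that this population is the denominator for prevalence.
2. Classify each person at the early time point, with the MDT process already planned, as ILD, ILA/indeterminate (including physiological impairment without ILD on imaging), or no ILD.
3. Define controls once, and state that respiratory symptoms alone do not disqualify a control. This settles the position of the non-hospitalised recruits.
4. Report case-control contrasts with and without the intermediate stratum, so that a strict comparison remains available.

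The cost is mainly drafting and one classification rule, if sites already follow everyone eligible under 4.2. If they have been following 1.2, somewhat more people will need follow-up within the 10,000 and 2,000 already planned; the documents do not allow that number to be estimated. Case-control contrasts may also be smaller once the middle group is included.

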2 STUDY OBJECTIVES

2.1 Primary objective

The primary objective of the study is to determine the prevalence of ILD at 12 months following SARS-CoV-2 infection and whether clinical severity correlates with severity of ILD in survivors.

2.2 Secondary objectives

1. to further define the PC-ILD population, in particular, to describe the emerging phenotypes and risk factors of PC-ILD
2. to determine the natural history of PC-ILD phenotypes longitudinally
3. to explore pathomechanisms of PC-ILD for candidate prognostic and theranostic biomarkers.

2.3 The primary endpoint

1. The primary endpoint of the study is as radiologically confirmed diagnosis of fibrotic or non-fibrotic ILD in the 12 months following COVID-19. Sub-studies will have a co-primary endpoint of change in the radiological extent of PC-ILD.

2.4 The secondary endpoints

- 1) progressive lung function impairment between 3 and 12 months, defined as $\geq 10\%$ relative decline in FVC, or $\geq 10\%$ relative decline in DLco, or increasing radiological extent of PC-ILD using image analysis [20].
- 2) Resolution of ILD, as defined by $\geq 10\%$ relative improvement in FVC, DLco, or reduction of radiological extent.

- 3) Persistence of ILD in those not meeting definition of progression or resolution
- 4) Presence of interstitial lung abnormalities (ILA) on radiological images that do not meet definition of ILD.
- 5) A comprehensive series of clinical, molecular, MRI and biochemical parameters will be assessed as biomarkers.

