3.1 Study procedures objectives and outcomes

	Objectives	Outcome Measures	Timepoint(s)
Primary	1) Examine and compare the prevalence of ILD in patients with varying severity of COVID-19. (Non-hospitalised will be compared with hospitalised patients and COVID severity defined as varying levels of respiratory support)	MDT diagnosis of ILD at 12 months (+/- 3 months) after acute infection	12 months (+/- 3 months) post SARS-CoV-2 NB: Need 2 time points, 6 months apart, between 3 and 15 months post-acute SARS-CoV-2
Secondary	Determine progressive lung function impairment between 3 and 12 months	Lung function decline: ≥10% relative decline in FVC or DLco OR Imaging deterioration: increasing radiological extent of PC-ILD using image analysis or MDT discussion	Need 2 time points, 6 months apart, between 3 and 15 months post-acute SARS-CoV-2
	Resolution of ILD	Any of the following: ≥10% relative improvement in FVC, DLco, or reduction of radiological extent.	12 months (+/- 3 months) post SARS-CoV-2 Need 2 time points, 6 months apart, between 3 and 15 months post-acute SARS-CoV-2
	Persistence of ILD in those not meeting definition of progression or resolution		12 months (+/- 3 months) post SARS-CoV-2 2 time points, 6 months apart, between 3 and 15 months post-acute SARS-CoV-2
	Persistence of ILAs		12 months (+/- 3 months) post SARS-CoV-2

			Need 2 time points, 6 months apart, between 3 and 15 months post-acute SARS-CoV-2
	In hospitalised patients only: Assess the relationship between initial severity of acute infection and ILD	Markers of severity of acute infection (e.g. CRP)	12 months (+/- 3 months) post SARS-CoV-2 Need 2 time points, 6 months apart, between 3 and 15 months post-acute SARS-CoV-2
	In hospitalised patients only Assess the impact of specific medical therapy used in the acute setting and ILD e.g. antivirals, immunomodulation	Medical therapy used for acute infection	12 months (+/- 3 months) post SARS-CoV-2 Need 2 time points, 6 months apart, between 3 and 15 months post-acute SARS-CoV-2
	Evaluate breathlessness, fatigue and cognition	Medical research council dyspnoea scale Dyspnoea 12 FACIT-F Montreal Cognition Assessment (MOCA)	3 month, 6 months (+/- 6 weeks) and 12 months (+/- 3 months) post SARS-CoV-2 infection
	Evaluate the quality of life of patients with COVID-19	Short Form-36 (SF-36) EQ5D-5L	3 month, 6 months (+/- 6 weeks) and 12 months (+/- 3 months) post SARS-CoV-2 infection

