6.4 Serious AEs

An SAE form should be completed and emailed to the Chief Investigator within 24 hours. However, relapse and death due to COVID -19, and hospitalisations for elective treatment of a pre-existing condition do not need reporting as SAEs.

All SAEs should be reported to the London Riverside REC where in the opinion of the Chief Investigator, the event was:

- 'related', ie resulted from the administration of any of the research procedures; and
- 'unexpected', ie an event that is not listed in the protocol as an expected occurrence

Reports of related and unexpected SAEs should be submitted within 15 days of the Chief Investigator becoming aware of the event, using the NRES SAE form for non-IMP studies. The Chief Investigator must also notify the Sponsor of all related and unexpected SAEs.

Local investigators should report any SAEs as required by their Local Research Ethics Committee, Sponsor and/or Research & Development Office.

Contact details for reporting [contact]**CI email (and contact details below)****Fax: N/A, attention [name]****Please send SAE forms to: [contact]****[contact] (Mon to Fri 09.00 – 17.00)****7.0 STATISTICS AND DATA ANALYSIS**

The prevalence of MDT-confirmed PC-ILD at both early (up to 6 months) and again at late (10-15 month) time-points and will be assessed within the total study population. The prevalence of broader radiological abnormalities and phenotypic patterns will also be assessed in a descriptive analysis, together with demographics, haematological and biochemical profiles, physiological performance, and patient-reported outcome measures. Analyses will be performed overall and stratified according to hospitalised and non-hospitalised, as well as severity of infection in hospitalised patients defined above.

Baseline and longitudinal changes in biomarkers reflecting PC-ILD evolution, including circulating factors and cell-types from detailed serological and cellular analysis, will be assessed in multilevel models for repeated measures to test associations according to the presence or absence of PC-ILD at late time points (10-15 months), and according to progression, resolution, or persistence of radiological patterns over follow up time points.

Analyses will be performed using standard epidemiological and statistical genetics methodology. This will include cross-sectional and longitudinal studies, and analyses of disease prevalence and incidence.

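### The 'Resolution of ILD' endpoint requires improvement, not absence of ILD, so participants who still have ILD at 12 months can be reported as resolved

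*Combined protocol and SAP*

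**What the plan says.** Section 2.4 counts ILD as resolved on a ≥10% "relative improvement in FVC, DLco, or reduction of radiological extent". The table in section 3.1 confirms that one component is enough: "Any of the following: ≥10% relative improvement in FVC, DLco, or reduction of radiological extent". Progression is the mirror image: a fall of at least 10% in FVC or DLco, or a growing extent. The third class takes whoever is left: "Persistence of ILD in those not meeting definition of progression or resolution".

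Whether ILD is present is assessed separately. The primary outcome measure in section 3.1 is "MDT diagnosis of ILD at 12 months (+/- 3 months) after acute infection". Section 7.0 plans to assess "The prevalence of MDT-confirmed PC-ILD at both early (up to 6 months) and again at late (10-15 month) time-points". Section 2.4 also lists, as its own endpoint, interstitial lung abnormalities (ILA) that fall short of ILD. The plan thus already has a boundary between ILD and not ILD, but the resolution endpoint does not use it.

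**The concern.** The criterion measures improvement and is labelled resolution. Section 2.4, section 3.1, section 7.0 and Appendix 1 contain no requirement that ILD, once diagnosed, has gone. A participant who improves but still has ILD is reported as resolved and is removed from the persistence class.

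Section 1.2 says the study must establish whether post-COVID ILD is reversible or becomes lasting or progressive fibrosis, and natural history is the second of the secondary objectives in section 2.2. The resolution and persistence rates are the direct answer to that question. A reader who sees a resolution rate will take it to mean that the disease cleared. The same report could also show the same people among those with ILD at 12 months.

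**Working it through.** The plan states no rate, variability or sample size for this endpoint, so there is no figure to reproduce. The check applies the rules as written.

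**Rules**
- Resolved: FVC change ≥ +10%, or DLco change ≥ +10%, or extent reduced.
- Progressed: FVC change ≤ −10%, or DLco change ≤ −10%, or extent increased.
- Persistent: neither of these.
- Primary outcome (section 3.1): MDT diagnosis of ILD at 12 months.

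**Example participants, all with ILD still present at 12 months** (values are invented)

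| Case | Change | Resolved | Progressed | Primary outcome |
|---|---|---|---|---|
| A | Extent 40% to 30%: (30−40)/40 = −25%; FVC and DLco flat | Yes | No | ILD |
| B | Extent 30% to 28%: −2/30 = −6.7%; FVC and DLco flat | Yes, if any reduction counts | No | ILD |
| C | Extent unchanged at 30%; DLco 50 to 55: +5/50 = +10% | Yes | No | ILD |

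Case A carries the argument. No measure moves against another, and the reduction exceeds 10% in relative terms, so the case does not depend on whether the 10% threshold also governs extent. B does depend on that. C shows that lung function alone can qualify with an unchanged scan.

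**Overlap with the primary outcome.** The overlap is a contradiction when the primary outcome is ILD at 12 months, as in sections 2.1 and 3.1. Section 2.3 is worded differently: "radiologically confirmed diagnosis of fibrotic or non-fibrotic ILD in the 12 months following COVID-19". If a diagnosis at any time in that period counted, someone could be a primary case and later clear without contradiction. The resolution label would still be wrong for case A.

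**Effect on the reported rates.** Take 100 people with early ILD. Let c clear, i improve with ILD still present, s stay stable and w worsen. Assume that those who clear qualify through reduced extent, that all i meet at least one component, and that nobody meets both resolution and progression.
- Resolved as written = c + i; persistent as written = s.
- Resolved if ILD must be absent = c; persistent in the plan's own sense (progressors excluded) = i + s.
- Share of the reported resolved group who still have ILD = i/(c + i).

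With c = 20, i = 40, s = 25, w = 15, the rule gives 20 + 40 = 60 resolved and 25 persistent. Requiring absence gives 20 resolved and 40 + 25 = 65 persistent. Progressed is 15 in both.

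The split is invented, so here is the range over i, with c = 20 and w = 15 held fixed and s = 65 − i:

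| i | Resolved as written | Persistent as written | Resolved group still with ILD |
|---|---|---|---|
| 0 | 20 | 65 | 0/20 = 0% |
| 10 | 30 | 55 | 10/30 = 33% |
| 20 | 40 | 45 | 20/40 = 50% |
| 40 | 60 | 25 | 40/60 = 67% |
| 65 | 85 | 0 | 65/85 = 76% |

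If absence is required, every row gives 20 resolved and 65 persistent.

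**Section 7.0.** The biomarker models compare participants "according to progression, resolution, or persistence of radiological patterns over follow up time points". If these groups follow section 2.4, the misclassification carries over. If they are purely radiological, a lung-function-only case such as C stays out, but the documents then do not define the groups.

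**The case against.** The strongest reply is that this is a secondary endpoint in an observational cohort and that nothing is lost. ILD at 12 months is assessed separately. Section 7.0 already plans MDT-confirmed prevalence early and late, so true clearance can be derived where both classifications exist. The same section also compares biomarkers by presence or absence of ILD at the late time points, and the resolution label cannot affect that comparison. As the mirror image of progression, the rule is a reasonable measure of direction of change. All of this stands. It limits the reach of the problem and makes it easy to correct, but it does not supply the missing criterion, and the endpoint that would be reported is still the one in section 2.4.

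A reader might infer more than the documents support:
- **That everyone with ILD at 12 months is called resolved.** Only those who meet a component are.
- **That the primary prevalence is biased.** It does not use the resolution rule.
- **That the three groups are the outcome in the biomarker models.** Section 7.0 models the biomarkers according to the groups, and ties the groups to radiological patterns.
- **That FVC or DLco gains reflect recovery from deconditioning.** Section 1.1 names deconditioning as a cause of breathlessness and says nothing of its effect on these measures.

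**Conclusion.** The concern holds. As written, participants who improve but still have ILD can be reported as resolved, and they leave the persistence class. The error runs one way: resolution is overstated and persistence understated, each by the number who improve with ILD still present and do not also meet progression.

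The documents do not give that number. In the invented split it is 40 of 100, which moves resolution from 20 to 60 and persistence from 65 to 25. It would be tempting to set the 25 against all 80 with ILD at 12 months (40 + 25 + 15), but that total includes the 15 progressors. The like-for-like contrast is 25 against 65. The biomarker comparisons are affected only to the extent that their groups use the section 2.4 definitions.

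**What to change.** In sections 2.4 and 3.1:
- Rename the present criterion 'Improvement'.
- Define 'Resolution' as MDT-confirmed ILD at the early time point and no MDT-confirmed ILD at the late one. Report separately those with residual ILA and those with neither ILD nor ILA, so that regression to ILA is visible.
- Define 'Persistence' as MDT-confirmed ILD at both time points, subdivided into improved, stable and progressive. Keep the existing progression endpoint.
- Restrict these endpoints to participants with early MDT-confirmed ILD and MDT classification at both time points, and report how many lack the pair.

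Use the same definitions for the groups in section 7.0.

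The text change is small because MDT assessment early and late is already planned. There are two costs. The reported resolution rate will be lower. The denominator will also shrink to those with paired classification, and pairs may be missing: Tier 1 is data only (section 4.2), section 3.3 collects images from clinical scans, CT is not in the visit lists of section 3.2.1, and section 2.2.4 of the image management protocol in Appendix 1 allows a single CT time point per patient.
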